# 11.2.2 Efficacy analyses

Efficacy of this combination will be measured by PSA progression-free survival (PFS), radiographic PFS, and maximal decline of PSA from baseline. PSA PFS, radiographic PFS, and time to maximal PSA decline will start at the first day of treatment and will be summarized by Kaplan-Meier. The numeric PSA value at maximal decline will be summarized by a boxplot and as a scatter plot of maximal decline by baseline PSA.

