## 4.3 Withdrawal of Subjects from Study Treatment and/or Study

#### Permanent discontinuation of either durvalumab plus tremelimumab or durvalumab.

An individual subject will not receive any further investigational product if any of the following occur in the subject in question:

- 1. Withdrawal of consent or lost to follow-up.
- 2. Adverse event that, in the opinion of the investigator or the sponsor, contraindicates further dosing.
- 3. Subject is determined to have met one or more of the exclusion criteria for study participation at study entry and continuing investigational therapy might constitute a safety risk.
- 4. Any AE that meets criteria for discontinuation as defined in the Dosing Modification and Toxicity Management Guidelines (see Table 3).
- 5. Subject noncompliance that, in the opinion of the investigator or sponsor, warrants withdrawal; eg, refusal to adhere to scheduled visits.
- 6. Initiation of alternative anticancer therapy including another investigational agent.
- 7. Confirmation of PD and investigator determination that the subject is no longer benefiting from treatment with durvalumab + tremelimumab.
- 8. Withdrawal of consent from further treatment with IP. The patient is, at any time, free to discontinue treatment, without prejudice to further treatment. A patient who discontinues treatment is normally expected to continue to participate in the study unless they specifically withdraw their consent to further participation in any study procedures and assessments

Subjects who are permanently discontinued from further receipt of investigational product, regardless of the reason (withdrawal of consent, due to an AE, other), will be identified as having permanently discontinued treatment.

Subjects who are permanently discontinued from receiving investigational product will be followed for safety per Section 10.1 and Table 2, including the collection of any protocol-specified blood specimens, unless consent is withdrawn or the subject is lost to follow-up or enrolled in another clinical study. All subjects will be followed for survival. Subjects who decline to return to the site for evaluations will be offered follow-up by phone per the schedule in table 2 as an alternative.

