### **9.3 PSA**

Samples for PSA will be collected and analyzed at the treating institution laboratory. PSA testing will be performed as per the schedule of assessment. The PSA test performed at the screening visit does not need to be repeated on C1D1 if visit occurs within 2 weeks of screening.

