## 9.4 Definition of progression of disease

For the purposes of this study, progression of disease (PD) is a composite endpoint, consisting of clinical deterioration and/or radiographic progression as defined below. Subjects with PSA progression alone will not be considered to have PD.

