# 11.1.2 Efficacy analysis set

To be evaluable for the secondary objectives, a patient needs to receive 2 doses of drug, have immune markers measured, and have at least one follow-up for clinical outcome measures. Patients who do not meet this level of evaluability will be described separately to establish any

trends in patient evaluability and comparability of compliant patients with the intended patient population based on available information.

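### Kaplan-Meier for time to maximal PSA decline has no event, censoring or non-decliner rule, so the curve depends on the coding chosen and on time on treatment

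*Combined protocol and SAP*

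**What the plan says.** Section 11.2.2 names the efficacy measures: "Efficacy of this combination will be measured by PSA progression-free survival (PFS), radiographic PFS, and maximal decline of PSA from baseline". It then sets the time-to-event summaries: "PSA PFS, radiographic PFS, and time to maximal PSA decline will start at the first day of treatment and will be summarized by Kaplan-Meier". The size of the decline is handled without survival methods: "The numeric PSA value at maximal decline will be summarized by a boxplot and as a scatter plot of maximal decline by baseline PSA".

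For time to maximal decline, the plan fixes only the starting point. Neither Section 11.2.2 nor any other section says:

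- what counts as the event;
- when a patient is censored;
- what happens to a patient whose PSA never drops below baseline;
- how much later PSA is needed before a minimum is accepted as the nadir.

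On sampling, Section 9.3 says: "PSA testing will be performed as per the schedule of assessment". Table 1 has PSA at screening and at every cycle from C1 to C13, which is every 4 weeks from week 0 to week 48. For patients who stop early, Section 4.3 says: "Subjects who are permanently discontinued from receiving investigational product will be followed for safety per Section 10.1 and Table 2". Table 2 has no PSA row. Under Section 11.1.2, a patient is evaluable after two doses, provided he also meets this condition: "have immune markers measured, and have at least one follow-up for clinical outcome measures".

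**The concern.** Progression can be dated from data available when it is declared. A nadir cannot: whether it has happened by a given week depends on every later PSA value. Kaplan-Meier needs an event, a risk set and censoring unrelated to outcome. Here every patient has some observed minimum, so taken literally nobody is censored. If instead patients still at their minimum when sampling ends are censored, that censoring follows the PSA course and the reason for stopping.

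The schedule makes this concrete. Planned PSA ends with treatment, and the reasons for stopping in Section 4.3 include adverse events, confirmed progression without continuing benefit, and a switch to other anticancer therapy. A patient whose PSA would have fallen until week 24, but who stops after the week-8 sample, is recorded with a nadir at week 8.

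Non-decliners are foreseeable. Section 1.0 describes two agents that prolong survival without lowering PSA, and Section 1.1 cites 0/17 responses to PD-1 blockade in this disease. These are not PSA-decline rates, but they show a group the plan needs to handle.

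At stake is a median that mixes non-response, speed of response, durability and length of monitoring. Section 11.3 intends these patients to inform the design of a later study, so such a median could be carried forward.

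**Working it through.** **The plan's own figure.** The documents give no number for this endpoint. The nearest is the Section 11.3 power for a Cox model of PSA PFS. With 20 × 0.75 = 15 events and coefficient 0.72, power is Φ(0.72 × √15 − 1.96) = Φ(0.83) = 79.6%. With 20 × 0.80 = 16 events and 0.70, it is Φ(0.70 × 4 − 1.96) = Φ(0.84) = 80.0%. Both reproduce the stated 80%, but neither bears on this point.

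**Illustrative simulation.** From the documents: PSA every 4 weeks, weeks 0 to 48. Everything else is assumed:

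- Half of patients are true decliners, with PSA relative to baseline f·exp(−kt) + (1 − f)·exp(gt). Here f is uniform on 0.3 to 0.9, k on 0.05 to 0.2 per week and g on 0.01 to 0.05 per week.
- The rest follow exp(gt).
- Assay noise has SD 0.08 on the log scale.
- Drop-out is 0 or 2% per week, unrelated to PSA, with at least one post-baseline value. At 2% per week, exp(−0.02 × 48) = 0.38 of patients reach week 48.
- There are 20,000 patients per scenario.

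The estimator is S(t) = Π(1 − d/n) over event times up to t. The median is the first time at which S is 0.5 or less.

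The four codings were:

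- A: every observed minimum is an event, with non-decliners at time 0.
- B: non-decliners are censored at the last PSA.
- C: decliners only, every minimum an event.
- D: as B, and minima at the last PSA are also censored.

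| Coding | Median, no drop-out | Median, 2%/week | Week-12 incidence, no drop-out | Week-12 incidence, 2%/week |
|---|---|---|---|---|
| A | 4 weeks | 4 weeks | 0.78 | 0.85 |
| B | 24 weeks | 16 weeks | 0.34 | 0.43 |
| C | 12 weeks | 8 weeks | 0.60 | 0.72 |
| D | 24 weeks | 28 weeks | 0.34 | 0.33 |

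Two separate gaps show up.

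1. Handling of non-decliners matters even with complete follow-up: the medians are 4, 24 and 12 weeks under A, B and C.
2. Handling of minima at the last PSA matters once patients leave early. The share of such minima rises from 0.00 to 0.14, and B and D separate from 24 and 24 weeks to 16 and 28.

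Under A, B and C, drop-out alone raises the week-12 incidence, so leaving early reads as reaching the nadir fast.

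**Sensitivity to the assumed decline rate** (48 weeks, 2% per week):

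- 30% true decliners: A 0 weeks, B not reached, C 8, D not reached.
- 80% true decliners: A 8 weeks, B 12, C 12, D 16.

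**The case against.** The strongest reply is that the curve can be perfectly sensible. If each decliner's PSA is followed until it has clearly risen, all nadir times are observed, and uncensored Kaplan-Meier is one minus their empirical distribution. The schedule helps: PSA is taken every cycle to week 48, and a rising PSA does not in itself count as progression, since "Subjects with PSA progression alone will not be considered to have PD". With no drop-out, essentially no simulated nadir fell at the last visit. This stands. A reader might infer that the curve can have no valid interpretation; the documents do not support that.

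A reader might also infer that the median must be 0 or undefined once half the patients fail to decline. That is not general. It is 0 if non-decliners are placed at time 0. Among decliners only it was 8 weeks even in the 30% scenario, where 59% had their minimum at baseline. If non-decliners are censored as they leave, the risk set shrinks and a median may still be reached.

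Nor can the documents support a figure for the share of nadirs at the last PSA. It went from 0.00 to 0.14 through the drop-out assumption alone.

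Finally, the summary is secondary in a pilot of about 20 evaluable patients with no formal hypotheses, and the boxplot and scatter plot already show the size of the decline. That also stands, and it limits the consequence. It does not supply the missing rules.

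**Conclusion.** The point holds in a limited form. As written, the Kaplan-Meier curve for time to maximal PSA decline is not defined, and the method invites dependence on post-hoc coding and on how long each patient stays on treatment. That much rests on the text alone: the missing rules in Section 11.2.2, PSA only to C13 in Table 1, and no PSA row in Table 2. Unscheduled PSA values taken for clinical reasons could narrow the gap, but the analysis plan does not rely on them.

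The size rests on assumptions. Under the middle scenario with drop-out, the median runs from 4 to 28 weeks and the week-12 incidence from 0.33 to 0.85 across codings. The simulated drop-out is heavy and unrelated to PSA, so the figures show sensitivity and do not predict this trial's result.

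The primary safety objective, the toxicity stopping rule, PSA PFS, radiographic PFS and the plots of decline size are unaffected. The change is worth making because it is cheap and because a later design may draw on these summaries.

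**What to change.** In Section 11.2.2, remove time to maximal PSA decline from the Kaplan-Meier sentence and keep PSA PFS and radiographic PFS there. In its place, report:

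- time of nadir (median, range) among patients with any PSA decline;
- the number who never declined;
- the number still at their minimum at the last PSA;
- best percent PSA change for all evaluable patients.

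The counts are needed because even the decliner-only median moved from 12 to 8 weeks with drop-out. Since Section 6.2.2 repeats the assessment schedule during retreatment, also state whether PSA from that period counts.

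If a time-to-event summary is wanted, use time to first PSA decline of a pre-set size, which can be dated when it occurs. State the censoring rule and how death and stopping treatment before the event are handled as competing events. The small downside is that its median may not be reached if few patients respond.

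The cost is a wording change, with no new data and no effect on sample size.

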#### 4.1 Inclusion criteria

For inclusion in the study, patients should fulfill the following criteria:

- 1. Written informed consent.
- 2. Age  $\geq$  18 years at time of study entry.
- 3. Eastern Cooperative Oncology Group (ECOG) performance status of 0 or 1.
- 4. Life expectancy of  $\geq$  52 weeks.
- 5. Adequate normal organ and marrow function as defined below:
  - Hemoglobin  $\geq 11.0 \text{ g/dL}$ .
  - Absolute neutrophil count (ANC) ≥ 1.5 x  $10^9$ /L (≥ 1500 per mm^3).
  - Platelet count ≥  $100 \times 10^9$ /L (≥ $100,000 \text{ per mm}^3$ ).
  - Serum bilirubin  $\leq 1.5$  x institutional upper limit of normal (ULN). This will not

apply to subjects with confirmed Gilbert's syndrome (persistent or recurrent hyperbilirubinemia that is predominantly unconjugated in the absence of hemolysis or hepatic pathology), who will be allowed only in consultation with their physician.

- AST (SGOT)/ALT (SGPT)  $\leq 2.5$  x institutional upper limit of normal
- Serum creatinine CL>40 mL/min by the Cockcroft-Gault formula (Cockcroft and Gault 1976) or by 24-hour urine collection for determination of creatinine clearance:

Males	
Creatinine CL =	Weight (kg) x (140 - Age)
(mL/min)	72 x serum creatinine (mg/dL)

- 6. Subject is willing and able to comply with the protocol for the duration of the study including undergoing treatment and scheduled visits and examinations including follow up.
- 7. Consent to MD Anderson laboratory protocol PA13-0291 and LAB02-152.
- 8. Willing to have peripheral blood mononuclear cells and bone marrow biopsies to be collected prior to receiving the first dose of durvalumab and tremelimumab, after 2-doses and 4-doses of durvalumab and tremelimumab, after 2nd treatment administration and 4th treatment administration.
- 9. Histologically or cytologically confirmed adenocarcinoma of the prostate.
- 10. Evidence of metastatic disease to the bone seen on most recent bone scan, CT scan and/or MRI.
- 11. Asymptomatic or minimally symptomatic patients (do not require narcotics for prostate cancer-related pain).
- 12. Tumor progression while on hormone therapy with castrate levels serum testosterone (≤ 1.7 nmol/L or 50 ng/dL) defined by PSA and/or radiographic criteria according to the Prostate Cancer Working Group 3 (PCWG3). Castrate levels of testosterone must be maintained by surgical or medical means throughout the conduct of the study.

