# 4.4 Replacement of subjects

A total of 20 biomarker-evaluable patients are planned to be enrolled on this trial. The number is small as a proof-of-concept study utilizing immune biomarkers as important secondary endpoints. To be evaluable for the secondary objectives, a patient needs to receive 2 doses of

durvalumab + tremelimumab, have immune markers measured, and have at least one follow-up for clinical outcome measures. Up to 7 patients who do not remain on study will be allowed to achieve 20 evaluable patients, for a maximum enrollment of 27 patients. All additional patients who received at least 1 dose of study drug will still be counted in safety analyses.

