# 11.3 Determination of sample size

The selection of 20 evaluable patients was intended as a pilot sample size with sufficient numbers to establish safety in this population as shown in Table 5 above while providing sufficient numbers for the secondary endpoints. This will allow investigation of a few marker endpoints and establish safety and feasibility of measuring the markers of interest while being able to accrue within 6 months. No formal hypotheses are planned. These patients will form the basis of designing a hypothesis-driven study in the future. However, we can make a statement about what might be detected in secondary endpoints at this sample size. The association between CD3 change and PSA PFS will be explored with a Cox model with CD3 as a continuous measure. Assuming that

75% (80%) of patients will progress by the end of the study, 20 patients will have 80% power to detect a regression coefficient of 0.72 (0.70) at a 2-sided 5% significance level, assuming the change in CD3 has a standard deviation of 1. The regression coefficient of 0.72 (0.70) is equivalent to a hazard ratio of 2.1 (2.0) or a doubling of risk per unit increase in CD3 (Calculations performed in NCSS-PASS 2005). This would hold true for both biomarker and any model of PSA PFS or Radiological/Clinical PFS.

Even if fewer than 20 patients have information available, this is the first look at these measures. Therefore, the descriptive information gathered on biological markers and outcomes, as well as the feasibility of collecting such information in future trials will be valuable.

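### The PSA boxplot is specified on the raw nadir value although the efficacy measure is decline from baseline; put it on a baseline-relative scale

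*Combined protocol and SAP*

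**What the plan says.** Section 11.2.2 defines the measures: "Efficacy of this combination will be measured by PSA progression-free survival (PFS), radiographic PFS, and maximal decline of PSA from baseline". The third is by its own wording a change relative to each patient's starting value.

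Two summaries of that measure's size follow in one sentence: "The numeric PSA value at maximal decline will be summarized by a boxplot and as a scatter plot of maximal decline by baseline PSA". Its timing is handled separately: "time to maximal PSA decline will start at the first day of treatment and will be summarized by Kaplan-Meier".

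Section 11.2.2 names no percent change, ratio to baseline, responder proportion or waterfall plot for PSA, and no other section supplies one. For tumor burden the protocol does take a relative view: Section 9.1.2 plans a graph of each subject's greatest percentage reduction against baseline.

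Table 1 schedules PSA at screening and at every cycle. Section 9.3 lets the screening value stand in for Cycle 1 Day 1 when the two fall within two weeks.

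**The concern.** The quantity named for the boxplot is a level, while the measure it is meant to summarise is a change. A nadir of 9 may follow a baseline of 10 or of 90, and the boxplot cannot tell these apart.

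A control arm would at least let nadir levels be compared between groups with similar starting values. Here there is one regimen (Section 3.1), and Sections 4.1 and 4.2 set no limits on baseline PSA.

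Efficacy is the first secondary objective (Section 2.2), and Section 11.3 says the data are to inform a later hypothesis-driven study. Since "No formal hypotheses are planned", the descriptive displays are the efficacy result for PSA decline. A designer who took the median from this boxplot would have a PSA level, not an estimate of how far PSA fell.

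**Working it through.** **1. Is there a figure to reproduce?** Not for this endpoint. The only power statement in Section 11.3 ("20 patients will have 80% power to detect a regression coefficient of 0.72 (0.70) at a 2-sided 5% significance level") concerns CD3 change and PSA PFS. It does reproduce: events = (z0.975 + z0.80)² / b² = 7.849 / 0.72² = 15.14, and 15.14 / 0.75 = 20.2 patients; 7.849 / 0.70² = 16.02, and 16.02 / 0.80 = 20.0 patients. It has no bearing on the PSA boxplot.

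**2. What the boxplot ranks.** Two illustrative patients (values chosen for the example, not taken from the documents):

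| Patient | Baseline | Nadir | Absolute decline | Percent change | ln(nadir/baseline) |
|---|---|---|---|---|---|
| A | 400 | 100 | 300 | -75% | -1.39 |
| B | 10 | 9 | 1 | -10% | -0.11 |

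On raw nadir, B (9) looks better than A (100). On percent change or log ratio, A has much the larger response. The reversal needs no distributional assumption.

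**3. What the scatter adds.** If decline is plotted in absolute units, A sits at (400, 300) and B at (10, 1), and the relative changes can be recovered: 300/400 = 75% and 1/10 = 10%. In those units decline = baseline × (1 − ratio), so a constant percent change appears as a rising line through the origin. If decline is plotted as a percentage, a constant percent change appears as a flat line. Section 11.2.2 does not say which scale is meant.

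**4. How much of the nadir spread is baseline.** Write log(nadir) = log(baseline) + log(nadir/baseline). If the two terms are independent, the baseline share of the variance is s_b² / (s_b² + s_r²), where s_b is the SD of log baseline and s_r the SD of the log ratio. The documents give neither SD, so these values are assumed:

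| s_b | s_r = 0.3 | 0.5 | 1.0 | 1.5 |
|---|---|---|---|---|
| 0.5 | 0.74 | 0.50 | 0.20 | 0.10 |
| 1.0 | 0.92 | 0.80 | 0.50 | 0.31 |
| 1.5 | 0.96 | 0.90 | 0.69 | 0.50 |

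For example, 1.0² / (1.0² + 0.5²) = 0.80. Baseline accounts for more than half only when s_b exceeds s_r.

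**5. Effect on the median at 20 patients.** This is a simulation of 20,000 trials per setting, assuming a median baseline of 20, a median nadir/baseline ratio of 0.8 and s_r = 0.5. As s_b rises through 0.5, 1.0 and 1.5, the central 95% range of the median nadir widens from 11.1–23.3 to 8.8–29.1 to 7.1–37.4. The range of the median percent change stays at about -38% or -39% to +5% throughout. The relative summary is unaffected by the baseline spread; the raw nadir is not. The size of the effect depends on the assumed inputs.

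**The case against.** The strongest reply is that the quoted sentence has two halves. The scatter shows each patient's decline together with his baseline, and with about 20 points every one is legible. So a reader who inferred that the plan gives only raw nadir values and no information relative to baseline would be wrong. This stands, and it confines the defect to the boxplot and to the unstated scale of the scatter.

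The boxplot phrase may also be loose wording for the size of the decline. That is possible. However, the same sentence names the decline separately for the scatter, so the literal reading is the natural one, and either reading calls for a correction to the text.

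A reader might go further and infer that the boxplot mostly displays baseline PSA. The documents do not support that: they give no distribution of baseline PSA or of response, and the share in step 4 ranges widely.

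Nor do they support rejecting the scatter for mathematical coupling. Coupling of this kind arises only if decline is in absolute units, and it would mislead mainly a correlation or regression of decline on baseline, which Section 11.2.2 does not plan.

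Finally, little depends on this endpoint. The primary objective is safety, no stopping rule or sample size uses PSA decline, Section 9.4 excludes PSA progression alone as disease progression, and percent change could be derived at reporting. All of that limits the consequence. It does not make the relative summary pre-specified.

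**Conclusion.** The point holds for the boxplot. As written, it summarises a PSA level where the stated measure is "maximal decline of PSA from baseline", and in a single-arm trial that level confounds starting PSA with response. This follows from the wording and the two-patient example alone. The scatter partly compensates, but its scale needs stating.

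The degree of confounding cannot be sized from the documents. The range of 0.10 to 0.96 rests on assumed SDs and on independence of baseline and response, and should not be quoted as a property of this trial.

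The consequence is modest: a descriptive secondary display, with no effect on the primary safety analysis or any decision rule. The change is still worth making, because the better summary uses data already scheduled.

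**What to change.** Amend Section 11.2.2 as follows.

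- **Boxplot (or waterfall plot):** show each patient's best percent change from baseline, or log(nadir/baseline). Include patients whose PSA never falls, shown at their smallest increase, so that the display is not restricted to those who declined.
- **Scatter:** plot the decline on a relative scale, or plot log nadir against log baseline with a no-change line. On log axes, parallel lines below the no-change line mark constant percent declines.
- **Baseline:** state which PSA value is used, given that Section 9.3 allows the screening value to replace Cycle 1 Day 1.

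Proportions of patients reaching a 30% or 50% decline are optional additions; neither threshold comes from the documents.

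The cost is a few lines of text. No visit, sample or data item is added. For a given patient, absolute and percent decline reach their maximum at the same visit, so the change of scale leaves the time-to-maximal-decline summary unchanged.
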